1.1.1 Primary purpose

To evaluate whether the main efficacy evaluation index of Probeam in radiation therapy for cancer patients

reached the target value of the disease control rate (DCR) 3 months after the end of the last treatment. Whether

the proportion of CTCAE grade 3 toxicity was lower than the acceptable value, and whether CTCAE grade 4 and

5 toxicity occurred.

1.1.2 Secondary purpose

To evaluate the secondary efficacy of Probeam in radiation therapy for cancer patients, objective response

rate (ORR), duration of response (DOR), DCR at 1 month after the end of last treatment, tumor markers (if

required), tumor-specific symptoms, The reality of the product usability assessment.

To evaluate the proportion of CTCAE grade 1 and 2 toxicity, laboratory tests, ECOG physical condition

classification, tumor recurrence rate, adverse event rate, serious adverse event rate, and device defect incidence

of Probeam in radiation therapy for cancer patients.

1.2 Trial design

This trial is a prospective, two-center, single-group target-value experimental design.

Prospective: Adopt a research approach that starts now and tracks the future. Prospective studies can clarify

the causal relationship, and there are unified standards for diagnosis, detection, and evaluation of the obtained

Confidential Information Page 3 / 17

Statistical Analysis Plan Version: V1.0

Date: 2022-11-11

data, so the data processing is controllable.

Two centers: 2 clinical trial institutions were selected to carry out the clinical trial. A higher number of cases

can be obtained in the same amount of time than a single-center trial, so the clinical trial time can be shortened.

Single-group target value method: Because the same device for investigational medical devices is

radioactive and difficult to obtain, the existing treatment methods are not feasible due to objective conditions, so

the single-group target value method is used. Moreover, the applicable population and main evaluation indicators

of experimental medical devices can be fully defined and relatively stable, and the main evaluation indicators

adopt the effective rate mentioned in the "Guiding Principles for the Technical Review of Clinical Evaluation of

Proton Carbon Ion Therapy Systems" (Circular No. 4 of 2018 of the State Food and Drug Administration), which

is relatively objective and reproducible. According to the Guidelines for the Technical Review of Clinical

Evaluation of Proton Carbon Therapy Systems, the target therapeutic rate of investigational medical devices

should be at least 80%, and the expected value is 95%. Among them, the effective definition is: CR+PR+SD

(complete response CR, partial response PR, and stable disease SD), which is basically consistent with the

definition of tumor disease control rate in this clinical trial. Therefore, no control group was set up in this clinical

trial, and a single-group target value method was used to evaluate whether the tumor disease control rate of

ProBeam reached the target value (80%), whether the proportion of CTCAE grade 3 toxicity, the main safety

evaluation index, was lower than the acceptable value (5%), and whether the proportion of CTCAE grade 4 and

5 toxicity was acceptable (0%).

1.3 Statistical assumptions

In this study, a single-group target-value experimental design was adopted, and the hypothesis test was as

follows:

H0: $\pi_1 \le \pi_0$; *H1*: $\pi_1 > \pi_0$

Test level $\alpha = 0.05$ (two-sided).

Among them, the disease $\pi_1\pi_0$ control rate and its target value of the ProBeam Proton Therapy System for

radiation therapy in cancer patients are respectively.

1.4 Number of subjects

This clinical trial intends to enroll 47 subjects. The sample size determination process is as follows:

This clinical study is a clinical validation design of a single group of target values, and the main effectiveness

indicator tumor disease control rate is the basis for sample size estimation. According to the "Guidelines for the

Technical Review of Clinical Evaluation of Proton Carbon Ion Therapy System" (Announcement No. 4 of 2018

Confidential Information Page 4 / 17

Statistical Analysis Plan Version: V1.0

Date: 2022-11-11

of the State Food and Drug Administration), the target value is set at 80%, the bilateral significance level is 0.05,

the power is 80%, and the sample size estimation professional software PASS 15.0 is used, and the sample size

of the experimental group is at least 42 cases calculated by the above parameters. Considering that about 10% of

the cases may be dropped out or lost to follow-up during the clinical validation, the sample size of the

experimental group was expanded to 47 cases.

In this trial, the two centers adopted competitive enrollment, and the investigators of the two centers were

diagnosed, operated and treated according to the requirements of relevant tumor diagnosis and treatment

guidelines, norms and consensus, and it is expected that there will be only a few patients in one center, and the

center will have little impact on efficacy and safety, and the center effect will no longer be considered in the

analysis.

2 Evaluation indicators

2.1 Effectiveness evaluation indicators

2.1.1 Key Effectiveness Indicators

• Tumor disease control rate (DCR) at 3 months after the end of last treatment

The occurrence of CR, PR and SD after the end of treatment was considered to be disease control, and the

absence of biochemical recurrence at the end of treatment of prostate cancer was considered to be disease control.

Proportion of subjects with disease control 3 months after the end of the last radiation therapy.

Calculation formula: DCR = number of subjects under disease control / total number of subjects \times 100%

2.1.2 Secondary effectiveness measures

• Objective response rate (ORR)

CR or PR was considered objective remission at the end of treatment, no biochemical recurrence

occurred at the end of prostate cancer at the end of treatment, and no regional lymph node metastasis or

distant metastasis was considered objective remission. Proportion of subjects with objective remission at

each time point after the end of the last treatment.

Calculation formula: ORR = number of subjects with objective remission / total number of subjects ×

100%

Time to Sustained Remission (DOR)

The time from the first assessment of the tumor as CR or PR to the first assessment of PD or death

from any cause.

Calculation formula: DOR = time to first assessment of PD or death from any cause - time to first

Confidential Information Page 5 / 17

Statistical Analysis Plan Version: V1.0
Date: 2022-11-11

assessment of CR or PR.

• Tumor disease control rate (DCR) at 1 month after the end of last treatment

The occurrence of CR, PR and SD after the end of treatment was considered to be disease control, and

the absence of biochemical recurrence at the end of treatment of prostate cancer was considered to be disease

control. Proportion of subjects with disease control 1 month after the end of the last treatment.

Calculation formula: DCR = number of subjects under disease control / total number of subjects ×

100%

Tumor markers (if required)

Tumor marker examination was performed and clinically significant changes in tumor markers (before

and after radiation therapy) were reported at the discretion of the investigator.

• Tumor-specific symptoms

Symptoms are recorded according to the type of disease, which may include, but are not limited to, the

following: pain, swallowing function, mobility, bleeding, visual acuity, appetite/weight, superficial lymph

node size, and clinically significant changes in reported symptoms (before and after radiation therapy) as

judged by the investigator.

• Ease of use (ProBeam System, Radiation Therapy Management Software (OIS), Radiation

Therapy Planning Software (Eclipse))

Investigators using the corresponding functions scored according to the Likert scale and collected open-

ended questions to evaluate the comprehensive feeling of ease of use during the treatment.

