DCR was calculated and the Clopper-Pearson method was used to calculate the 95% confidence interval for tumor disease control. ORR was calculated and the Clopper-Pearson method was used to calculate the objective response rate 95% confidence interval. Descriptive statistics on the percentage change from baseline of the measurable sum of the longest diameter (SLD). The Waterfall Chart was made by the maximum percentage reduction in SLD per participant compared to the screening period.

The Kaplan-Meier method was used to calculate the median duration of response,

Statisticalmedian progression-free survival, median survival, and overall survival, and plotted K-analysisM curves (long-term follow-up data).

Safey analysis

Descriptive statistics were used to classify organ systems in MedDRA medical terms, and the incidence, occurrence, and severity of adverse events, adverse reactions, and serious adverse events were summarized.

Laboratory indicators, ECOG physical status grading and other safety-related indicators were compared and evaluated before and after treatment, and clinical evaluation [no clinical significance, clinically significant (tends to normal), clinically significant (tends to be abnormal), not checked], CTCAE grade evaluation before and after treatment cross-tab.

The central effect is considered in the analysis process, and the general linear model is used for the measurement data and CMH for the counting data.

The baseline data analysis was performed using the Full Analysis Set (FAS); Effectiveness analysis uses FAS and Per Protocol Set (PPS); Security analysis uses the Safety Set (SS).

Trial flowchart

The body of the protocol

1 Sponsor information

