Definition of indicators: CR or PR after the end of treatment is considered objective remission, prostate cancer has no biochemical recurrence at the end of the last treatment, and no regional lymph nodes or distant metastasis are considered objective remission. Proportion of participants who experienced objective remission at each time point after the end of the last treatment.

Metric type: Qualitative.

Data collection time: screening period, 1 month \pm 7 days, 3 months, \pm 7 days after the end of the last treatment.

Evaluation time: 1 month \pm 7 days, 3 months, \pm 7 days after the last treatment.

Site of evaluation: Tumor receiving radiation therapy.

Evaluation method: The changes in tumor CT or MRI imaging before and after treatment were evaluated by an independent imaging review panel according to RECIST 1.1. At 3 months of radiographic evaluation, if PD is found, PET-CT is required to confirm it.

Calculation formula: ORR = number of subjects in objective response / total number of subjects × 100%.

Criteria: See RECIST 1.1 for details. At the time of 3-month imaging evaluation, if the patient is found to have PD, PET-CT examination is required to confirm it, if progress is confirmed, it is recorded as PD, if progress cannot be confirmed, it may be false progression, and it is recorded as SD. If prostate cancer does not have biochemical recurrence, PET-CT examination is not required, and there is no metastasis by default, which is regarded as objective remission, and if biochemical recurrence occurs, it is regarded as not objectively remission, and PET-CT is required to confirm tumor metastasis.

Note: Participants who aborted the trial for any reason (other than loss to follow-up) before the end of the last radiotherapy were considered to have not responded objectively. Disease site evaluation uses the same approach as baseline, including consistent contrasted/non-contrast scans and prompt scanning. If changes are needed, the case must be discussed with a radiologist to determine whether an alternative approach is possible. If not, the objective situation in the future is unclear.

(2) Time to sustained remission (DOR).

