Reason for selection: The Guidelines for the Review of Clinical Evaluation Technologies of Proton Carbon Ion Therapy Systems (CFDA Circular No. 4 [2018]) recommends the use of the latest version of the commonly used evaluation criteria for radiation oncology as the clinical trial evaluation criteria, so RECIST 1.1 is used Relevant indicators as effectiveness evaluation criteria; Due to the particularity of the disease, the evaluation method recommended in the relevant diagnosis and treatment

guidelines is selected. They are all commonly used indicators for the evaluation of tumor treatment effects, and are widely recognized and applied by clinicians.

Indicator definition: the time between the first assessment of the tumour as CR or PR and the time between the first assessment of PD or death from any cause.

Indicator type: quantitative.

Data collection time: 1 month \pm 7 days, 3 months, \pm 7 days after the end of the screening period, until tumor progression or subject death.

Evaluation time: 3 months \pm 7 days after the last treatment.

Site of evaluation: Tumor receiving radiation therapy.

Evaluation method: The changes in tumor CT or MRI imaging before and after treatment were evaluated by an independent imaging review panel according to RECIST 1.1. At 3 months of radiographic evaluation, if PD is found, PET-CT is required to confirm it.

Calculation formula: DOR = time to death from PD or any cause on the first assessment - time to CR or PR for the first assessment;

Criteria: See RECIST 1.1 for details. At the time of 3-month imaging evaluation, if the patient is found to have PD, PET-CT examination is required to confirm it, if progress is confirmed, it is recorded as PD, if progress cannot be confirmed, it may be false progression, and it is recorded as SD.

Note: If no tumor progression or death is observed during the follow-up period after the end of radiotherapy, the formula is: DOR > last visit time after the end of the last radiotherapy - CR or PR time for first assessment. Others are the same as ORR.

(3) Tumor disease control rate (DCR).

Reason for selection: DCR 3 months after the end of the last treatment was the primary evaluation index, and DCR at other follow-up time was used as a secondary evaluation index.

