ECOG	Eastern Cooperative Oncology Group	Eastern Oncology Collaborative Group
FAS	Full Analysis Set	Full analysis set
ICH	The International Council for Harmonisation of Technical Requirement for Pharmaceuticals for Human Use	International Harmonization Council for Technical Requirements for Pharmaceuticals for Human Use
MedDRA	Medical Dictionary for Regulatory Activities	Medical Dictionary of Regulatory Activities
NYHA	New York Heart Association	New York Heart Society
OIS	Oncology Information System	Oncology Information System
ORR	Objective Response Rate	Objective response rate
PD	Progressive Disease	Disease progression
PET	Positron Emission Tomography	Positron emission tomography
PN	Preferred Name	Preferred name
PPS	Per-Protocol Set	Conforms to the scenario set
PR	Partial Response	Partial relief
PSA	Prostate Specific Antigen	Prostate-specific antigens
PT	Preferred Terms	Preferred term
SAE	Serious Adverse Events	Serious adverse events
SAP	Statistical Analysis Plan	Statistical analysis plan
SAS	Statistical Analysis System	Statistical analysis system
SD	Stable Disease	Stable disease
SLD	Sum of Longest Diameter	Sum of longest diameters of tumors
SOC	System Organ Class	Systematic organ classification
SS	Safety Set	Security datasets
TEAE	Treatment Emergent Adverse Event	Adverse events during the treatment period
TNM	Tumor, Node, Metastasis	Tumors, lymph nodes, metastases
WHODD	World Health Organization Drug Dictionary	World Health Organization Dictionary of Medicines

Page 1 / 17 Confidential Information

WOCF Worst Observation Carried Forward Worst observed data carryover

Confidential Information Page 2 / 17

Statistical Analysis Plan Version: V1.0

Date: 2022-11-11

This statistical analysis plan (SAP) refers to the E9 guiding principles of the International Council for

Harmonization of Technical Requirements for Pharmaceuticals for Human Use (ICH) Guidance for Industry:

Statistical Principles for Clinical Trials ICH E3 Guidance for Industry: Structure and Content of Clinical Study

Reports Relevant national regulations and guidelines, according to the clinical study protocol titled "Varian

ProBeam Proton Therapy System China Clinical Trial (Hefei)" (version number: V1.4, Version Date: 2022-06-

10) developed.

This SAP describes the rules for the presentation and analysis of short-term follow-up efficacy data and

safety evaluation data specified in the protocol, and describes in detail the data, variables and statistical methods

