4.3 Effectiveness indicators are missing

When analysing the main effectiveness evaluation indicators based on PPS, it is not necessary to consider filling them.

In the sensitivity analysis of the main effectiveness evaluation indicators based on FAS, the missing values of the main effectiveness evaluation indicators were not filled.

The missing values of qualitative secondary effectiveness evaluation indicators ORR and DCR were filled by the method of worst observational data carryover (WOCF).

The missing value of the quantitative secondary effectiveness evaluation index DOR was not filled.

Other secondary effectiveness evaluation indicators, such as tumor markers, tumor-specific symptoms, and

Confidential Information Page 9 / 17

rsion: V1.0 Date: 2022-11-11

product ease of use, were not filled.

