5.4.2 Secondary effectiveness measures

Secondary effectiveness assessments were based on the full analysis set (FAS) and the permissible set (PPS).

• Objective response rate (ORR)

• Time to Sustained Remission (DOR)

Tumor disease control rate (DCR) at 1 month during follow-up period

• Tumor markers (if required)

Tumor-specific symptoms

• Ease of use (ProBeam System, Oncology Information System (OIS), Treatment Planning System

(Eclipse))

The 95% confidence interval was calculated by Clopper-Pearson for the above secondary efficacy indicators

of "objective response rate (ORR)" and "tumor disease control rate (DCR) during the follow-up period of 1

month".

For the "time to sustained response (DOR)" secondary efficacy measure, describe the sustained response.

Descriptive statistics were performed on the percentage of measurable tumor longest diameter sum (SLD)

from baseline, and a waterfall chart was made for the maximum percentage reduction of SLD in each subject

compared with the screening period.

For the secondary efficacy indicators of "tumor markers" and "tumor-specific symptoms", the changes

before and after are described, and the changes are described in the table.

For the secondary efficacy index of "product ease of use", the scores of each category and the total score

were calculated, and the details of the open questions were described in a table.

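### The short-term SAP gives a duration of response only to responders who progress or die and does not carry over the protocol's rule for those still in response

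*SAP*

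**What the plan says.** **SAP.** Section 2.1.2 gives one formula, "Calculation formula: DOR = time to first assessment of PD or death from any cause - time to first" assessment of CR or PR (the sentence runs over a page break). It has no branch for a responder who has neither progressed nor died. Section 4.3 adds: "The missing value of the quantitative secondary effectiveness evaluation index DOR was not filled". For the analysis, section 5.4.2 says only, for this "secondary efficacy measure, describe the sustained response". Section 5.2 sets the default for continuous variables: number of cases, mean, standard deviation, median, quartiles, minimum and maximum. The SAP names no censoring rule and no Kaplan-Meier analysis. It is confined to short-term follow-up. Section 6, on changes from the protocol's analysis plan, deals only with missing adverse event severity and relatedness.

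**Protocol.** Section 3.1.4.2 (2) classes DOR as quantitative, evaluates it 3 months after the last treatment, and covers the missing case in a note: "If no tumor progression or death is observed during the follow-up period after the end of radiotherapy", then "DOR > last visit time after the end of the last radiotherapy - CR or PR time for first assessment". The protocol's statistical methods (summary and section 4.7.1) also state: "The Kaplan-Meier method was used to calculate the median duration of response". That sentence ends with a tag that limits it to long-term follow-up data.

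**The concern.** An ongoing response is a right-censored observation: its duration is known to exceed a certain length. The SAP formula gives it no value, and the next instruction that applies is the one on missing DOR. A programmer who reads sections 2.1.2, 4.3, 5.2 and 5.4.2 in order could compute DOR for responders with an event, leave the others blank, and report a mean and median of what remains. That summary is conditional on failing within the short window. Responders who do well drop out of a measure meant to show how long responses last.

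The SAP text matters because protocol section 4.8 says that, normally, only analyses agreed in advance in the SAP appear in the trial report, and later additions are exploratory. A censored analysis added after the data are seen would lose its prespecified standing.

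**Working it through.** **Plan's own figure.** The documents give no figure for DOR. The sample size of 42, raised to 47, rests on the disease control rate and plays no part here.

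**Inputs from the documents.** Response is imaged 1 month and 3 months after the last treatment, each within 7 days (protocol 3.1.4.2 (1), to which the DOR note refers for other matters). The formula and the missing-value rule are those in SAP 2.1.2 and 4.3.

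**Inputs assumed.** Exponential DOR with true median m of 3, 6, 12, 24 or 60 months; response first seen at month 1; 2 months of observation after that; 20 responders where a count is needed. None of these is in the documents.

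**Step 1: range of a scan-to-scan value.** With a month of 30.4375 days, the interval from the 1-month to the 3-month scan is 2 × 30.4375 = 60.9 days. Both windows can shift it by 7 days, so it runs from 60.9 − 14 = 46.9 to 60.9 + 14 = 74.9 days, or about 47 to 75. A death, or progression found at an unscheduled visit, could give a shorter value. A responder first seen at month 3 has almost no time in which to record an event.

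**Step 2: share of responders with a value.** With λ = ln 2 / m, the share is P = 1 − exp(−2λ) = 1 − 2^(−2/m). For m = 12, P = 1 − 2^(−1/6) = 0.109.

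**Step 3: mean of the recorded values.** With exact event times, the mean given an event within 2 months is 1/λ − 2·exp(−2λ)/P. For m = 12 this is 17.31 − 2 × 0.891/0.109 = 0.98 months. If progression is found only at the 3-month scan, each value is about 2 months.

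**Step 4: what a censored analysis would show.** With 20 responders all observed for 2 months, a Kaplan-Meier median is reached if at least 10 have an event, with probability P(Binomial(20, P) ≥ 10).

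| True median (months) | True mean | Share with a value | Expected values among 20 | Chance of no value among 20 | Mean of recorded values, exact times | Chance that median is reached |
|---|---|---|---|---|---|---|
| 3 | 4.3 | 37.0% | 7.4 | <0.001 | 0.92 | 0.17 |
| 6 | 8.7 | 20.6% | 4.1 | 0.010 | 0.96 | 0.003 |
| 12 | 17.3 | 10.9% | 2.2 | 0.099 | 0.98 | <0.0001 |
| 24 | 34.6 | 5.6% | 1.1 | 0.315 | 0.99 | <0.0001 |
| 60 | 86.6 | 2.3% | 0.5 | 0.630 | 1.00 | <0.0001 |

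The recorded mean stays near 1 month (or near 2 months if scan-detected) while the true mean rises twentyfold. As a check, censoring the event-free responders at 2 months and fitting an exponential model to simulated trials, pooled, returned medians of 3.0, 6.0, 11.9, 23.7 and 59.9 months. The loss of information comes from dropping those responders, not from the short window alone.

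**The case against.** The best defence is that the governing rule exists. The SAP says it was developed from protocol V1.4, section 6 declares no change to DOR, and the SAP shortens other endpoint definitions too. One can read the protocol's note as still in force. Nor does leaving missing DOR unfilled exclude anyone by itself: protocol section 4.7.2 also declines to estimate missing DOR, alongside the note that records event-free responders as exceeding their follow-up. The absence of Kaplan-Meier from a short-term SAP also fits the protocol's long-term tag.

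Section 5.4.2, moreover, orders no mean or median. A listing that marks ongoing responses would satisfy it without bias.

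These points limit the finding. A reader might infer that the trial has no rule for event-free responders, or that the SAP prescribes a biased mean. The documents support neither: the protocol has the rule, and the bias arises only if the section 5.2 default is applied. What remains is that the SAP, which controls the short-term analysis, states a formula that cannot be applied to those responders, does not point to the protocol's note, and has a default that leads to the wrong summary.

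A reader might also infer from the 95% expectation that about 5% of responders would have a value. That does not follow. The 95% is an expected control rate among all subjects. It counts stable disease, while stopping early (other than through loss to follow-up) counts as failure. It is not an event-free rate among responders.

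**Conclusion.** The point stands as a gap between SAP and protocol that should be closed. If DOR is summarised by the SAP's default, the summary covers only early failures. A scan-to-scan value is about 47 to 75 days whatever the true durability, and that range rests only on the visit schedule.

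The share of responders represented, about 37% down to 2%, depends on the assumed exponential distribution, on true medians of 3 to 60 months, and on first response at month 1. The direction does not depend on them: leaving out responders whose response is unfinished can only shorten the summary, compared with following the same responders to their events.

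It would be wrong to infer that the trial's main result is at risk. DOR is secondary and descriptive, protocol section 4.5 attaches no success criterion to it, and the decision on disease control is unaffected.

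**What to change.** - **SAP 2.1.2:** add the protocol's branch. A responder without progression or death is right-censored at the last visit after radiotherapy. Censoring at the last tumour assessment is also defensible, but it differs from the protocol's last visit and would have to be declared in SAP section 6.
- **SAP 5.4.2:** report the numbers of responders, events and ongoing responses, with a Kaplan-Meier estimate of DOR, shown as 'not reached' where that applies, in place of an event-only mean or median. Since the protocol tags Kaplan-Meier for long-term data, section 6 should note its short-term use.
- **SAP 4.3:** a clause saying that an ongoing response is censored, not missing, would remove the remaining ambiguity.

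The cost is a few lines of text and one standard SAS procedure. The downside is that the short-term median will usually be 'not reached', as Step 4 shows, so the count of ongoing responses will be the informative result.
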